#### Footnotes:

- a Visits 7 to 13 may occur  $\pm$  2 days from scheduled visit
- b Visits 2-5 hospitalization may be extended at the discretion of the investigator Hospitalization on Visits 6 and 7 are at the discretion of the investigator to ensure per-protocol ECG assessment and PK sampling are done Hospitalization includes admission to a hospital or the utilization of an inpatient facility
- c Vital signs (blood pressure, heart rate, respiratory rate, and oral or aural body temperature) obtained after the patient is resting in supine position for ≥ 5 minutes Vital signs during hospitalization are assessed pre-dose within 30 minutes of dosing, and at about 4 hours post dosing All other assessments are at about 4 hours post dosing
- d Height only at Screening Visit; Patients will be weighed clothed (lightly) and without shoes at every indicated visit
- Scheduled ECG recordings (in triplicate) should be obtained after the patient is resting in supine position for ≥ 10 minutes. Three triplicate ECG assessments (9 assessments) should be performed on Day -1 to serve as the Baseline value. Scheduled ECG recording during hospitalization (Visits 4 through 7 and Visit 11) should be done prior to the planned PK sample at pre-dose within 30 minutes of dosing, and at the approximate time of maximum plasma concentration of both MIN-101 (6 to 8 hours post dosing) and BFB-520 (9 to 12 hours post dosing). Scheduled ECG recordings on Visits 8 to 10 should be done prior to the planned PK sample 2-4 hours post dosing after all other assessments have been completed.
- f Safety laboratory tests include haematology, serum chemistry (including serum lipid profile, and fasting blood glucose) and prolactin Patients must fast for 8 hours before the blood sample is taken Baseline safety laboratory tests will be performed no later than Day -2 (and not earlier than Day -5) to ensure results are available prior to the first study drug administration
- E Dipstick urinalysis will be completed on site at Screening, Baseline, and Weeks 4, 8, 12 (or early termination) Urine specimen will only be sent to the central laboratory for microscopic analysis in the event the dipstick results are abnormal

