## 3.3.7. Presentations by Time Point

Visit designations used in statistical analyses will be derived by aligning actual visit dates within visit date windows as shown in Table 1. If assessments are collected multiple times within a given visit window, the result closest to the target day will be used for summary presentations. If two measurements have the same distance to the target day, the earlier value will be used. All planned, Unscheduled, and Early Termination assessments will be categorized similarly. All assessments will be presented in the listings.

Table 1 Visit Designations

Derived Visit	Scheduled Visit (Day a )	a Target Day						
Baseline	Day -1		Days [-28, 1] and prior to first dose of study drug					
Day 1	Day 1	1	Day [1]					
Day 2	Day 2	2	Day [2]					
Week 1	Week 1	8	Days [3,11]					
Week 2	Week 2	15	Days [12, 18]					
Week 3	Week 3	22	Days [19, 25]					
Week 4	Week 4	29	Days [26, 43]					

Derived Visit	Scheduled Visit (Day a )	Target Day	Window [lower bound, upper bound] b				
Week 8	Week 8	57	Days [44, 71]				
Week 12 End of double- blind treatment period c	Week 12	85	Days 72 through last day of double-blind treatment period.  Final or termination visit during the double-blind treatment phase				
Week 12.1	Week 12 + 1	87	First day of open-label treatment				
Week 12.2	Week 12 + 2	88	First day of open-label treatment + 1				
Week 13	Week 13	92	First day of open-label treatment + 2 through Day 9				
Week 14	Week 14	99	Days [96, 102]				
Week 15	Week 15	106	Days [103, 109]				
Week 16	Week 16	113	Days [110, 127]				
Week 20	Week 20	141	Days [128, 155]				
Week 24	Week 24	169	Days [156, 183]				
Week 28	Week 28	197	Days [184, 211]				
Week 32	Week 32	225	Days [212, 239]				
Week 36	Week 36	253	Days [240, 267]				
Week 40	Week 40	281	Days [268, 295]				
Week 44	Week 44	309	Days [296, 323]				
Week 48	Week 48	337	Days [323, 351]				
Week 52	Week 52	365	Days [352, 372]				
Week 54 EOS period c			Final or termination visit during the open-label treatment period; date will be earlier if early study termination occurred.				

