a Relative to the date of the first dose of double-blind investigational product. For example, Day 1 = the date of the first dose of double-blind investigational product. The lower and upper bounds reach approximately halfway between the windows. For example, weekly visit series use windows that are [-3 days,+3 days] surrounding each target day. However, visit windows leave no gaps in time for assessments to be uncategorized.

b Visit day is calculated as (visit date – date of the first dose of double-blind investigational product + 1) if the visit date is on or after the date of the first dose of double-blind investigational product. Otherwise, it's calculated as (visit date – date of the first dose of double-blind investigational product).

e Presented in analysis tables for safety parameters, including but not limited to electrocardiographic parameters, clinical laboratories, and vital signs.

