## 3.3.8. Definitions and Terminology

#### Baseline Value

Baseline will be defined as the last valid evaluation done before the study drug administration on Day 1. For ECG, the mean of the 3 triplicate ECG assessments (9 assessments) performed on Day -1 will serve as the Baseline value.

#### Day 1

Day 1 is the earliest day that study drug is first initiated.

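### As written, SAP Table 1 and its tie rule select the Day 1 pre-dose vital signs, which are also Baseline, so the by-visit Day 1 change is zero wherever that reading exists

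*SAP*

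**What the plan says.** SAP 3.3.7 derives visits by placing actual visit dates in the windows of Table 1. When a window holds several results, "the result closest to the target day will be used for summary presentations". The next sentence settles ties: "If two measurements have the same distance to the target day, the earlier value will be used".

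The Baseline row of Table 1 covers "Days [-28, 1] and prior to first dose of study drug". The Day 1 row has target day 1 and a window of Day 1 alone, with no condition that the assessment follow the dose. SAP 3.3.8 adds: "Baseline will be defined as the last valid evaluation done before the study drug administration on Day 1". ECG is treated differently: "For ECG, the mean of the 3 triplicate ECG assessments (9 assessments) performed on Day -1 will serve as the Baseline value".

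Footnote c of the double-blind schedule (SAP 1.2) reads: "Vital signs during hospitalization are assessed pre-dose within 30 minutes of dosing, and at about 4 hours post dosing". All other vital-sign assessments are at about 4 hours after dosing. SAP 5.4.4 presents vital signs and their changes by time point and treatment group, without naming pre-dose and 4 hours as separate rows.

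Two other rows of Table 1 need attention. The Week 13 window is printed as "First day of open-label treatment + 2 through Day 9", although the footnotes count days from the first double-blind dose and state that "visit windows leave no gaps in time for assessments to be uncategorized". Week 44 is Days 296 to 323 and Week 48 is Days 323 to 351.

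**The concern.** On Day 1 every patient is an inpatient, so two vital-sign readings fall on one date. If the rule that picks one value per window is applied to them, it returns the reading that already serves as Baseline, and the change is a value minus itself. The Day 1 row of the blood-pressure and pulse change table would then carry no information about the hours after the first dose.

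A second effect follows at later visits. Inpatient visits would contribute a pre-dose reading and outpatient visits a reading at about 4 hours. A by-visit profile would then mix two times relative to dosing. At Weeks 1, 2, 13 and 14, where hospitalisation is at the investigator's discretion, the mix could occur between patients within one visit.

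**Working it through.** **Day 1 vital signs**

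1. Readings on Day 1: pre-dose, V(pre), and about 4 hours after dosing, V(4h) (SAP 1.2, footnote c).
2. Baseline is the last valid evaluation before dosing, and its window runs to Day 1 (SAP 3.3.8; Table 1). When V(pre) is valid, Baseline = V(pre).
3. Visit day is computed from dates (Table 1, footnote b), so both readings have distance |1 - 1| = 0 from the target.
4. The tie goes to the earlier value, so the Day 1 value = V(pre).
5. Day 1 change = V(pre) - V(pre) = 0, whatever V(4h) is.

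An illustration with invented systolic values: V(pre) = 120 and V(4h) = 112. The rule gives 120 - 120 = 0. A Day 1 window limited to post-dose readings gives 112 - 120 = -8. If V(pre) is missing and the Day -1 reading is 122, Baseline is 122, the Day 1 value is 112, and the change is 112 - 122 = -10. The zero therefore depends on a valid Day 1 pre-dose reading.

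**Which reading is kept at each visit**

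| Visit | Setting | Reading kept |
|---|---|---|
| Day 1 | inpatient | pre-dose (also Baseline) |
| Day 2 | inpatient | pre-dose |
| Weeks 1, 2 | investigator's discretion | pre-dose if inpatient, otherwise about 4 h |
| Weeks 3, 4, 8 | outpatient | about 4 h |
| Week 12 | inpatient | pre-dose |
| Weeks 12.1, 12.2 | inpatient | pre-dose |
| Weeks 13, 14 | investigator's discretion | pre-dose if inpatient, otherwise about 4 h |

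Eight double-blind treatment visits have vital signs: Days 1 and 2, and Weeks 1, 2, 3, 4, 8 and 12. The pre-dose reading is kept at Day 1, Day 2 and Week 12, which is 3 of 8. If Weeks 1 and 2 are inpatient, it is 3 + 2 = 5 of 8.

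**Week 13 bound**

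Take open-label treatment to start on Day 87, the target day that Table 1 gives for Week 12.1.

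- Lower bound: 87 + 2 = 89.
- Upper bound as printed: Day 9. Counted from the first double-blind dose, the window is empty and Days 89 to 95 belong to no visit, contrary to the footnote.
- Upper bound from footnote a (weekly target plus or minus 3): 92 + 3 = 95. Week 14 starts at Day 96, so there is no gap.
- Upper bound if Day 9 means open-label Day 9: 87 + 8 = 95. A start on Day 86 gives 94 and leaves 1 day uncovered. A start on Day 88 gives 96 and overlaps Week 14 by 1 day.

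**Day 323**

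Enumerating Days 1 to 372 with the Week 13 bound set to 95 leaves no gaps and one overlap, Day 323. That day is midway between the two targets: 323 - 309 = 14 and 337 - 323 = 14. Elsewhere Table 1 gives the midpoint to the earlier visit. For example, Day 295 lies midway between the Week 40 target (281) and the Week 44 target (309), and belongs to Week 40. By that pattern Week 48 should start at Day 324.

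**The case against.** The strongest reply is that SAP 5.4.4 governs vital signs and already keeps the two readings apart. It presents them by time point and says three readings are recorded at each assessment time point, which makes a time point a reading occasion. Protocol 10.8.3 likewise refers to each scheduled time point, and footnote c schedules two on inpatient days. Applied literally to all same-day data, the tie rule would also discard two readings of each triplicate, against the averaging in 5.4.4. It would discard the ECGs near peak concentration too, against the visit-and-timepoint wording for the QTcF ANCOVA in 5.4.5. On this view the rule was never meant for same-day repeats.

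This shows that a programmer might build the table sensibly, but not that the SAP tells them to. Section 3.3.7, which holds the tie rule, is itself titled as presentations by time point. Laboratory tables carry the same phrase although no within-day laboratory repeats are scheduled. Where the SAP wants timepoints within a visit, in the QTcF ANCOVA, it says so; for vital signs it does not. Two programmers could follow the text and produce different tables.

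Other parts of the reply stand. All assessments are listed, potentially clinically significant post-Baseline vital signs are tabulated separately, and dizziness or syncope is tabulated as an adverse event of special interest. The Week 13 bound may simply have lost a digit when the PDF was read. The Day 323 overlap is trivial: with visits allowed plus or minus 2 days, Week 44 falls on Days 307 to 311 and Week 48 on Days 335 to 339, so no on-schedule visit lands there.

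**Conclusion.** The point holds as a defect of wording with a definite consequence. If 3.3.7 is applied to vital signs as written, the by-visit Day 1 change is exactly 0 for every patient with a valid Day 1 pre-dose reading, and later by-visit summaries can mix pre-dose and 4-hour readings. This rests on reading the one-value-per-window rule as covering vital signs. It lapses if 5.4.4 is taken to mean separate pre-dose and 4-hour rows. The reach is limited to descriptive safety summaries.

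A reader might infer more, but the documents do not support it:

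- *Zero for all patients and all parameters.* A patient without a valid Day 1 pre-dose reading has an earlier Baseline, and ECG Baseline is the Day -1 mean.
- *A postural-hypotension signal is hidden.* Scheduled vital signs are supine (Protocol 8.4), so neither reading measures a postural drop. The dose-limiting events were at single 32 mg doses of the immediate-release form; Protocol 1.4.1.2 reports none with multiple doses, and 1.4.2.3 none in the patient-study summary.
- *The first week on MIN-101 is lost for crossover patients.* Weeks 12.1 and 12.2 have their own windows. At most the Week 13 visit is unassigned, and only if the printed bound is genuine.
- *Efficacy is affected.* PANSS and PSP are not scheduled on Day 1 or at Week 13, so the primary and key secondary analyses do not depend on these rows.

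**What to change.** In SAP Table 1 and section 3.3.7:

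1. Restrict the Day 1 window to assessments after the first dose of study drug.
2. State in 5.4.4 that vital signs are summarised by nominal within-day timepoint (pre-dose, about 4 hours) within each derived visit, and that the closest-day and tie rules apply only after that assignment.
3. Confirm the Week 13 upper bound as Day 95, counted from the first double-blind dose.
4. Start the Week 48 window at Day 324.

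The cost is a few words in the SAP and some extra rows in the vital-sign tables. No data collection, visit schedule or efficacy analysis changes.

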#### Last Dose of Study Drug (Double-Blind Phase)

Last Dose of Study Drug (Double-Blind Phase) is defined as the last date a patient received study drug during the double-blind phase (up to Week 12).

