## Treatment-emergent Adverse Event

Any recorded adverse event that occurs on or after the initiation of study treatment and less than or equal to 14 days after the last dose of treatment is considered treatment-emergent. Additionally, it is assumed that an adverse event which was reported to have started on Day 1 without an associated onset time may have occurred after the initiation study treatment. Hence, adverse events occurring on Day 1 without an onset time are assumed to be treatment emergent.

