#### 5.4.5. ECG Assessments

ECG measurements will be provided by a central reader.

ECGs are recorded in triplicate one minute apart, and all ECG analyses will be based on the average of triplicate measurements. The mean of the 3 triplicates (9 assessments) performed on Day -1 will be used as the Baseline for all analyses of that safety parameter.

ECG variables and their change from Baseline will be summarized with descriptive statistics by time point and treatment group. ECG variables will include heart rate, PR interval, RR interval, QRS interval, QT interval, and QTc interval corrected for heart rate using Fridericia's correction, QTcF.

QTcF values will also be tabulated for their absolute values and tabulated relative to Baseline measurements in order to detect individual QTcF changes. Additionally, the number and percentage of patients who meet the PCS values defined in Table 6 will be summarized.

Table 6 Criteria for Potentially Clinically Significant ECG Parameters

			Criteria
Parameter	Flag Observed Value		Change from Baseline or Observed Value
Heart Data (hous)	High	> 110	
Heart Rate (bpm)	Low	≤ 50	
QTcF a Interval (msec)	High Male	> 450	>30-60, > 60, > 450-480,
Q'Tel' Interval (insee)	High Female	> 470	> 480-500, > 500
QRS Interval (msec)	High	> 120	
PR Interval (msec)	High	> 220	

<sup>a QTc interval is derived as: QTcF=QT Interval (msec) / (RR (msec)/1000)(1/3)

To understand the effect of treatment arm on the change in QTcF, an ANCOVA will be performed by assessment times (visit and timepoint within visit) using the change from Baseline (as dependent variable) with treatment arm (MIN-101 32 mg, MIN-101 64 mg, and placebo) as a factor, and Baseline value as covariate. Estimates for the difference at each assessment time for each dose group versus placebo, standard error of the mean, and the upper bound of the 2-sided 90% confidence intervals will be presented.

Important abnormalities in ECG waveform that are changes from Baseline readings will also be reported in a listing, as well as PCS ECG parameters.

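### ECGs taken after study drug has stopped can enter the by-visit QTcF summaries, because SAP 3.3.7 windows them by study day alone and SAP 5.4.5 sets no time-since-last-dose condition

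*SAP*

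**What the plan says.** SAP 3.3.7 assigns assessments to derived visits by study day. On early termination it says: "All planned, Unscheduled, and Early Termination assessments will be categorized similarly". When several results fall in one window, "the result closest to the target day will be used for summary presentations", with ties going to the earlier value. A footnote to SAP Table 1 adds that "visit windows leave no gaps in time for assessments to be uncategorized".

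The Table 1 entry for Week 12 and the end of the double-blind period runs from Day 72 to the last day of that period. It also takes in the "Final or termination visit during the double-blind treatment phase". The footnote to the end-of-period label reads: "Presented in analysis tables for safety parameters, including but not limited to electrocardiographic parameters, clinical laboratories, and vital signs".

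SAP 5.4.5 gives descriptive ECG summaries by time point and a QTcF ANCOVA at each visit and each timepoint within it, with treatment arm and Baseline in the model. Neither carries a last-dose condition. Protocol 10.8.4 has the same model, also without one. The Safety population (SAP 4.3) is defined by having taken a dose and by treatment received, with no time limit.

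Protocol 9.2 requires an attempt at the Visit 11 assessments when a patient stops treatment early, and Protocol 3.1 asks for them as soon as possible. Under rules 8 and 9 of Protocol 9.3, drug is withheld while a long QTcF is checked by the central reader, and the patient is withdrawn only if it is confirmed.

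**The concern.** The plan expects ECGs from patients who have already stopped drug and gives no rule that separates them from on-drug ECGs. Suppose the last dose is on Day 70 and the termination visit on Day 77. That ECG belongs to the end-of-double-blind entry, alongside Visit 11 ECGs from completers who were dosed that morning. Unscheduled ECGs taken during a rule 8 or 9 drug hold are treated in the same way.

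The ECG times for Visit 11 are set relative to a dose (Time and Events Schedule, double-blind phase, footnote e). A patient who has stopped takes no dose, and the SAP does not say which within-visit timepoint that ECG receives.

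Protocol 1.5 identifies QT prolongation as a dose-related risk and lists specific measures against it. Drug-arm ECGs taken off drug carry less of the effect, so mixing them in would be expected to understate the by-visit difference from placebo. For a safety analysis that is the unfavourable direction.

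**Working it through.** Neither document states a figure for the QTcF difference or for off-drug ECGs, so there is no plan figure to reproduce. The check is a bound.

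**Inputs**
- Phase 2b completion: 244 randomised, 165 completed the double-blind phase (Protocol 1.4.2, Table 2). Non-completers: 244 − 165 = 79, and 79/244 = 32.4%.
- QTcF effect: mean change below 10 msec after Day 28 in CYR-101C01 (Protocol 1.4.2.3). This comes from an older formulation and is not placebo-corrected.
- Assumed: a fraction q of terminators attend off drug with no effect left, the rest contribute no ECG, and termination is equal across arms and unrelated to QTcF.

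**End-of-double-blind row.** The off-drug share is f = 79q / (165 + 79q). The expected difference is the true difference × (1 − f), so the shift toward zero is below 10 × f.

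| q | f | Shift below (msec) |
|---|---|---|
| 10% | 7.9/172.9 = 4.6% | 0.5 |
| 25% | 19.75/184.75 = 10.7% | 1.1 |
| 50% | 39.5/204.5 = 19.3% | 1.9 |
| 100% | 79/244 = 32.4% | 3.2 |

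**Scheduled rows.** The Table 1 windows and the closest-to-target rule were applied to simulated patients. Dropout was at a constant hazard totalling 32.4% or 40% over 84 days. The 40% is the SAP 3.1 inflation rate, which is defined by missing efficacy data and is used here only as a dropout scenario. Every terminator has an ECG 2 or 7 days after the last dose, and scheduled visits fall on their target days. The Week 12 window is left open to the termination ECG.

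| Row | Off-drug share | Shift on a true 10 msec |
|---|---|---|
| Weeks 1–4 | 1.9–5.9% | 0.2–0.6 |
| Week 8 | 6.8–11.5% | 0.7–1.2 |
| Week 12 (as its own row) | 6.7–11.5% | 0.7–1.2 |

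If only a quarter of terminators attend, the largest share falls to 0.25 × 0.115 / (0.25 × 0.115 + 0.885) = 3.1%, or about 0.3 msec.

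**Displacement of an on-drug ECG.** For Visits 7 to 11 the scheduled ECG lies within −2 to +2 days of target. A later off-drug ECG replaces it only if strictly closer to target. The widest gap is from −2 to +1, or 3 days, so this is a minor route.

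**Residual drug.** No correction is made. Protocol 1.4.1.1 gives a parent half-life of 6.4 to 8.1 hours and reports similar findings for BFB-520, yet it also reports BFB-520 accumulation above 2-fold on daily dosing. The documents do not settle how quickly the QT effect fades. Any residual effect lowers the shifts above.

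**The case against.** The strongest reply has five parts.

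1. **The row is labelled.** The end-of-period entry openly includes terminators. If the entry is two rows run together, the Week 12 row is bounded by the last day of the double-blind period. This stands in part. It limits the Week 12 row, but the windows for Weeks 1 to 8 have no such bound, and a label does not tell the reader how many ECGs in the row were off drug.

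2. **The ANCOVA is not shown to be affected.** A reader might infer that the post-dose cells near peak concentration are diluted. The documents do not support that. An undosed ECG has no defined timepoint, and the footnote mentions analysis tables, not ANCOVA cells. This stands.

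3. **The lag is meant to be short.** Termination visits are due as soon as possible, and some patients will still be dosing. This stands, and makes a seven-day gap an illustration only.

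4. **The adverse-event rule is no precedent.** Events "less than or equal to 14 days after the last dose of treatment is considered treatment-emergent", a convention that would keep the Day 77 ECG. This stands. The rule shows only that the SAP uses last-dose limits elsewhere; it does not supply one for ECGs.

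5. **Exclusion can bias too.** A patient withdrawn for a rise above 60 msec may still exceed the arm mean days later, so removing that ECG could lower the mean. The direction is therefore an expectation, not a certainty. It is not a reason to leave the rule undefined, provided those ECGs are summarised separately and stay in the outlier counts.

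**Conclusion.** The gap is real: nothing in SAP 3.3.7 or 5.4.5 keeps off-drug ECGs out of the by-visit QTcF summaries. It matters mainly for the end-of-double-blind row and less for the scheduled rows. It reaches the ANCOVA only if such ECGs are given a timepoint.

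The likely effect is small. It is about 1 msec in the most exposed row if 25% of terminators attend off drug, and near 3 msec if all do with no drug effect left. Attendance, lag since last dose and the true QTcF difference for the new formulation are not in the documents. The bound also assumes that termination is unrelated to QTcF; if patients with the longest QTcF are the ones stopped, the dilution could be larger.

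A reader might infer that the trial's QT assessment is compromised. The documents do not support that. Threshold counts keep any peak recorded on drug. Concentration-QTcF modelling (Protocol 8.3.3 and 10.9, SAP 7) uses measured concentrations. The timed ECG sets recorded at Visits 4 to 7 still measure the early effect, although the Week 1 and Week 2 rows could also pick up a few termination ECGs. No threshold or decision in either document depends on the by-visit results, and the stopping rules and DSMB act independently. Priority is minor.

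**What to change.** Change the SAP only, in 3.3.7 and 5.4.5:

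- Flag each ECG as on-treatment by a prespecified time since last dose. The limit must exceed the once-daily dosing interval, so that ordinary pre-dose ECGs stay in, and should be set with BFB-520 elimination in mind.
- Restrict the by-visit QTcF summaries, the ANCOVA and the closest-to-target choice to flagged ECGs.
- Summarise off-drug termination ECGs separately by days since last dose, and keep them in the outlier counts.
- State which Table 1 row and which timepoint take a termination ECG.

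The cost is a few sentences and some programming. The last-dose date is already defined in SAP 3.3.8, and intake times are in the patient diaries (Protocol 7). Each row will have slightly fewer records. The restriction does not remove the informative loss of patients withdrawn for QTcF, so the separate summary must keep them visible. The ECG schedule at the termination visit should stay as it is: cutting it would need a protocol amendment and would lose QT data in patients who have stopped.
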